10.1. Adverse Events

10.1.1. Definition of Adverse Event

An Adverse Event (AE) is defined as any untoward medical occurrence, unintended disease or injury, or untoward clinical signs (including abnormal laboratory findings) in patients, users or other persons, whether or not related to the investigational medical device. (ISO 14155:2011 3.2)

The following information regarding each AE will be obtained: date and time of onset and resolution (duration), severity, whether it was serious, any required treatment or action taken, outcome, relationship to the investigational device, relationship to the procedure, and whether the AE caused withdrawal from the study. Hypoglycemic events, as defined in the protocol, will be summarized and compared between the 2 randomized treatment groups.

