Study Design	
This is a multicenter, single-arm, open-label study conducted in Australia.
 
Twenty (20) participants will be enrolled initially and up to 60 participants may be enrolled in the non-insulin (NIS) Cohort. The first 30 participants will be treated with the first-generation catheter (Gen 1) and the next 20-30 participants will be treated with the second-generation catheter (Gen 2). Patients who sign the informed consent and are deemed eligible following a general and endoscopic screening will be enrolled in the study.
 
Patients with T2D inadequately controlled on 1-4 non-insulin glucose-lowering medication(s) will be screened for study eligibility. Eligible patients who consent to participate in the study will maintain his/her background anti-diabetic medication(s) stable (no medication or dose change) for at least 12 weeks prior to baseline visit.
 
The index procedure will be performed under general anesthesia or deep sedation and within 28 days from the baseline visit. Patients will undergo an endoscopic screening immediately prior to the index procedure. The index procedure will be performed under fluoroscopic and endoscopic guidance. Patients may be discharged the same day per the local hospital's guideline. A patient is enrolled in the study when an energy delivery is attempted. Patients excluded during endoscopic screening will be considered screen failure and will be followed for four weeks after the procedure for safety.
 
Post index procedure, participant will be on a transitional diet consisting of clear liquids for 24 hours followed by full liquid diet for 3 days, pureed food for 3 day, and soft food for one week.
 
Background medication(s) may be decreased peri-procedurally per Section 6.2.2 but will be titrated to the pre-procedure dose and maintained for 24 weeks post index procedure and during the transitional diet period. After the 24-week follow-up visit, participants will be managed according to the current guidelines of American Diabetes Association and their glucose-lowering medications will be optimized to

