3. INTRODUCTION

This statistical analysis plan (SAP) describes the planned statistical methods to be used during the reporting and analysis of data collected under the Clinical Investigation Protocol entitled *Safety and Feasibility of Endoscopic Application of a Novel Therapy for Duodenal Mucosal Regeneration in the Treatment of Type II Diabetes (REGENT-1-US Study)*, Doc. No. 346. This SAP should be read in conjunction with the study protocol and case report forms (CRFs).

The REGENT-1-US study is a multicenter, open-label, treatment-only study conducted in Australia. The study is designed to assess the feasibility and preliminary safety of the Endogenex device for endoscopic duodenal cellular regeneration in patients with type 2 diabetes (T2D) inadequately controlled on glucose-lowering medications. The protocol enrolled patients who were treated with non-insulin glucose-lowering agents; a tabulation of the treatment and number of patients is presented below.

Device Generation 1 / 600 Volts / Single Treatment (n)	Device Generation 1 / 600 Volts / Double Treatment (n)	Device Generation 2 / 750 Volts / Double Treatment (n)	All Patients (n)
3	7	10	20

This plan is developed for analysis and reporting of the 48-week follow up data. The SAP may be revised in the future to address additional follow up data analysis beyond 48 weeks, if necessary.

Patients are considered enrolled in the study once the patient has passed endoscopic screening and proceeded to the Index procedure. **Screen failures** are defined as patients who consented to participate in the clinical study and started the screening tests specified by the protocol but are not subsequently enrolled into the study. Procedure success was defined as at least 6cm of duodenum was successfully treated.

The following analysis populations are defined for the presentation of the results from this study: *Intent-to-Treat* (ITT), *Full Analysis Set* (FAS) [referred to in the study protocol as the modified Intent-to-Treat (mITT) population], *Per-Protocol* (PP) and *Completed Cases* (CC). (Ref. Section 11.3 of the study protocol).

The primary and secondary safety analyses will be performed using the ITT population. The primary effectiveness analyses will be performed using the FAS population. The Per-Protocol population and Completed-Cases population will be used for the sensitivity analyses of the primary and secondary effectiveness endpoints.

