5. STUDY OVERVIEW

5.1. Study Design and Description of the Study Device

This is a multicenter, open-label, treatment-only study conducted in the United States. A total of 20 participants is planned for the study. The study will test two treatment parameters. The first 10 participants will be treated at a generator setting of 600 Volts/13 bursts/350 KHz (600V) and the second group of 10 participants at 750 Volts/8 bursts/350KHz (750V). In the 600V group, the first 5 participants will be enrolled/treated with the investigational device sequentially with at least 14 days observation time between each procedure. In the 750V group, the first participants will be enrolled/treated with the investigational device sequentially with at least 6 days observation time between each procedure.

Participants with T2D inadequately controlled on 2-3 non-insulin glucose-lowering medication(s) will be screened for study eligibility. Eligible participants who consent to participate in the study will maintain his/her background glucose-lowering medication(s) stable (no medication or dose change) for at least 12 weeks prior to baseline visit.

The index procedure will be performed under general anesthesia or deep sedation and within 21 days from the baseline visit. Participants will undergo endoscopic screening immediately prior to the DMR procedure, and eligible participants will undergo the DMR procedure. Participants may be discharged per local hospital's guideline; an overnight stay is not required but allowed per local policy and investigator's clinical judgement. A participant is enrolled in the study when the Endogenex catheter insertion is attempted. Participants excluded during endoscopic screening will be considered a screen failure and will be followed for four weeks after the procedure for safety.

Post index procedure, participants will be on a transitional diet consisting of clear liquids for 24 hours followed by a full liquid diet for 3 days, pureed food for 3 days, and soft food for one week, and then return to normal food as tolerated.

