The *Level 3* display will be used for summarizing the parameters recorded multiple times during the follow-up visits. An example of the layout is presented below; rows will be repeated for all visits where a measurement is recorded using the expanded time windows.

Level 3a Display

Parameter and Statistic	Observation Time	Device Generation 1 / 600 Volts / Single Treatment	Device Generation 1 / 600 Volts / Double Treatment	Device Generation 2 / 750 Volts / Double Treatment	All Patients
HbA1c	Baseline				
HbA1c	Post-Procedure Visit xxx				
HbA1c	Change from Baseline				

Level 3b Display

Parameter and Statistic	Observation Time	Device Generation 1 / 600 Volts / Single Treatment	Device Generation 1 / 600 Volts / Double Treatment and Device Generation 2 / 750 Volts / Double Treatment	All Patients
HbA1c	Baseline			
HbA1c	Post-Procedure Visit xxx			
HbA1c	Change from Baseline			

There will be 2 sets of comparative analyses prepared, each predicated on different combinations of device generation, voltage, and single vs. double treatment. The planned comparisons are outlined below.

Comparison Set 1

Device Generation 1 / 600 Volts / Single Treatment vs.

Device Generation 1 / 600 Volts / Double Treatment vs.

Device Generation 2 / 750 Volts / Double Treatment

Comparison Set 2

Device Generation 1 / 600 Volts / Single Treatment vs.

Device Generation 1 / 600 Volts / Double Treatment plus Device Generation 2 / 750 Volts / Double Treatment

Supportive individual patient data Listings will be sorted and presented by site number, patient number and visit date, if applicable. Listings will also include the number of days relative to the DMR index procedure. Specific algorithms are discussed for imputing missing or partially missing data, if deemed appropriate, under specific data topics. Imputed or derived data will be flagged in the individual patient data Listings. Imputed data, restricted to dates, will not be incorporated into any raw or primary datasets from the electronic capture system. The imputed data will be retained in the derived / analysis datasets.

Summary statistics will consist of the number and percentage of responses or counts at each level for categorical variables (e.g. race). For continuous variables, and the sample size (n), mean, median, standard deviation (SD), minimum, and maximum values will be presented.

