Table 14.3.4 entitled *Summary of Post-Procedural Adverse Events by Event Type and Relationship to the Study Device (ITT Population)* provides the presentation of adverse events by relationship to study device. This table will have the same structure as that of Table 14.3.2, however, only those adverse events that were determined to be related to study device will be displayed. Patients with multiple occurrences of the same event will be summarized using the strongest relationship to study device. The number and percentage of patients experiencing each event type will be displayed.

Table 14.3.4a entitled *Summary of Post-Procedural Adverse Events by Event Type and Relationship to the Study Device by Device Generation, Voltage, and Single vs. Double Treatment (ITT Population)* provides the presentation of adverse events by relationship. This table will follow the Level 2a format for the IS population and Level 2b format for the population. Patients with multiple occurrences of the same event will be summarized using the strongest relationship to study device. The number and percentage of patients experiencing each event type will be displayed.

Table 14.3.5 entitled *Summary of Post-Procedural Adverse Events by Event Type and Relationship to the Study Procedure (ITT Population)* provides the presentation of adverse events related to the study procedure. This table will have the same structure as that of Table 14.3.2, however, only those adverse events that were determined to be related to the study procedure will be displayed. Patients with multiple occurrences of the same event will be summarized using the strongest relationship to study procedure. The number and percentage of patients experiencing each event type will be displayed.

Table 14.3.5a entitled *Summary of Post-Procedural Adverse Events by Event Type and Relationship to the Study Procedure by Device Generation, Voltage, and Single vs. Double Treatment (ITT Population)* provides the presentation of adverse events by relationship. This table

will follow the Level 2a format for the IS population and Level 2b format for the population. Patients with multiple occurrences of the same event will be summarized using the strongest relationship to study device. The number and percentage of patients experiencing each event type will be displayed.

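### SAP 10.1.1 compares hypoglycemia between two randomized groups, but nothing is randomized and the split is not named; by-group Tables 14.3.5a and 14.3.5.1a choose among repeat events on the device scale

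*SAP*

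**What the plan says.** **Hypoglycemia.** SAP Section 10.1.1, at the end of the adverse event definition, says: "Hypoglycemic events, as defined in the protocol, will be summarized and compared between the 2 randomized treatment groups". SAP Section 5.1 describes the design as follows: "This is a multicenter, open-label, treatment-only study conducted in the United States". The protocol supplied (No. 196) says in its summary and in Section 4.1: "This is a multicenter, single-arm, open-label study conducted in Australia". SAP Section 5.1 gives the 600 V setting to the first ten participants and the 750 V setting to the second ten. Section 3 tabulates three groups by device generation, voltage and single or double treatment (3, 7 and 10 patients). Section 7 adds: "There will be 2 sets of comparative analyses prepared". Set 1 compares the three groups; Set 2 compares the single-treatment group with the other two combined.

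**Relationship tables.** SAP Section 4.2 records relationship to device (AEDREL) and relationship to procedure (AEPREL) as separate variables, and Section 10.1.3 asks for them to be presented separately. For Table 14.3.5 (procedure, all patients) the rule is: "Patients with multiple occurrences of the same event will be summarized using the strongest relationship to study procedure". For Table 14.3.5a, the same table by group, the rule is: "Patients with multiple occurrences of the same event will be summarized using the strongest relationship to study device". Table 14.3.5.1 (device or procedure, all patients) uses the strongest relationship to either; its by-group version, 14.3.5.1a, again uses the device only.

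**The concern.** Both are analysis rules that a programmer would follow, not background text.

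The hypoglycemia sentence claims a design property that the study lacks and leaves the comparison open. More than one split fits, so the choice could be made after the data are seen, which a SAP exists to prevent. Section 10 names hypoglycemia as a safety topic, and Section 3 says the planned analyses may go into regulatory submissions and manuscripts.

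In the two by-group tables, the rule for repeat events works on a different scale from the one in the title. The scales can diverge by design: Protocol Section 9.2 lists events known to be related to anesthesia or upper GI endoscopy under the unlikely-related category for the device. Those are the events a procedure-relationship table is meant to show.

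**Working it through.** **1. Group counts.** From SAP Section 3: 3 + 7 + 10 = 20 patients. At 600 V, 3 + 7 = 10; at 750 V, 10. This reproduces the 10 per group and 20 in total of SAP Section 5.3. No power calculation is stated, so there is none to check.

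**2. Splits the hypoglycemia sentence could mean.**

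| Reading | Source | Sizes | Two groups? | Randomized? |
|---|---|---|---|---|
| 600 V v 750 V | SAP 5.1, 5.3 | 10 v 10 | yes | no, enrollment order |
| Comparison Set 2 | SAP 7 | 3 v 17 | yes | no |
| Comparison Set 1 | SAP 7 | 3 v 7 v 10 | no | no |

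Two readings fit the number two. The third is a defined comparison but has three groups. None is randomized.

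**3. Does the choice matter?** The documents give no by-group hypoglycemia counts. As an assumption for illustration only, let 1 of 3, 1 of 7 and 4 of 10 patients have an event.

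- By voltage: (1 + 1)/(3 + 7) = 2/10 = 20% at 600 V; 4/10 = 40% at 750 V.
- By Comparison Set 2: 1/3 = 33% single treatment; (1 + 4)/(7 + 10) = 5/17 = 29% double treatment.

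The direction reverses. Fisher's exact p is 0.63 for the first split and 1.0 for the second, so neither would be persuasive, but the reported pattern depends on the split.

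Precision also differs by split. With zero events, the exact two-sided 95% upper limit is 1 − 0.025^(1/n):

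| n | 3 | 7 | 10 | 17 | 20 |
|---|---|---|---|---|---|
| upper limit | 70.8% | 41.0% | 30.8% | 19.5% | 16.8% |

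**4. Rules for repeat occurrences in SAP 10.1.3, side by side.**

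| Table | Relationship in title | Display | Rule uses | Agrees? |
|---|---|---|---|---|
| 14.3.4 | device | overall | device | yes |
| 14.3.4a | device | by group | device | yes |
| 14.3.5 | procedure | overall | procedure | yes |
| 14.3.5a | procedure | by group | device | **no** |
| 14.3.5.1 | device or procedure | overall | device or procedure | yes |
| 14.3.5.1a | device or procedure | by group | device | **no** |

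The sentence is the same in all three by-group tables and correct only in 14.3.4a, which suggests it was carried over from there.

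**5. Effect on one patient (constructed example).** The same event occurs twice: occurrence A is graded possibly related to device and unlikely related to procedure; occurrence B is graded unlikely related to device and definitely related to procedure.

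- Table 14.3.5 takes the strongest procedure grade: B, definitely related.
- Table 14.3.5a takes the strongest device grade: A. The patient appears as unlikely related if A's procedure grade is shown, or as possibly related if its device grade is shown.
- Table 14.3.5.1 takes the stronger of either scale: definitely related.
- Table 14.3.5.1a takes A, whose strongest grade is possibly related.

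On either reading, the by-group table disagrees with its overall counterpart. A patient with a single occurrence is outside the rule.

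**The case against.** The strongest reply is that these are two drafting slips in a small feasibility study. SAP Sections 3 and 5.1 call it open-label and treatment-only, Section 7.1 says testing is for information only, and Section 9 says there are no formal hypothesis tests. Table columns are labelled by device generation, voltage and treatment number. Both relationship variables go into the listing, and the Level 2 displays carry an all-patients column, so a mismatch with Table 14.3.5 could be seen and traced.

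Much of that stands, and it rules out several stronger readings that a reader might infer:

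- *The comparison cannot be run at all.* Two-group splits exist; what is missing is randomization and a statement of which split applies.
- *A group difference will be reported as randomized evidence.* One sentence does not show that, given how the rest of the SAP describes the design.
- *All three groups were treated in sequence.* Order is documented for 600 V then 750 V, not for the 3 single and 7 double treatments within 600 V.
- *All procedure-related events are misgraded.* The rule covers only repeat occurrences of the same event in a patient.
- *The serious-event tables carry the error.* Section 10.1.4 says the tables are repeated for serious events, but its list contains no by-group version, so this is unclear.
- *Sore throat shows the size.* The 59% in Protocol Appendix 4 comes from 27 patients under protocol 196, not the SAP's 20 under Doc. No. 346. It pools device- and procedure-related events and says nothing about repeats.

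What does not stand is the idea that feasibility status excuses the wording. It excuses low power, not a randomization claim, an unnamed split or the wrong variable.

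**Conclusion.** The point holds in limited form. The hypoglycemia comparison rests on randomization that neither document describes, and it is not determined: 10 v 10, 3 v 17 and 3 v 7 v 10 are all candidates. Two by-group tables, 14.3.5a and 14.3.5.1a, contradict their own titles and their overall counterparts on how repeat events are graded.

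The number of patients misgraded cannot be computed from the documents and may be small or zero. The primary endpoint is unaffected: SAP Sections 9 and 9.1 define it separately, as any device- or procedure-related serious event through day 84.

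Two assumptions apply. The absence of randomization rests first on the SAP's own Sections 3 and 5.1, because the SAP names a different document number from the protocol supplied. The hypoglycemia definitions that the SAP refers to are taken to be those in Appendix 1 of the supplied protocol.

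**What to change.** 1. In SAP 10.1.1, delete *randomized* and the count of two. State that hypoglycemic events, in every category the protocol defines (Appendix 1: Levels 1 to 3, severe, documented symptomatic, probable symptomatic), are summarized by the Comparison Set groups of SAP Section 7 and overall, with the groups labelled as non-randomized.
2. In the rule for Table 14.3.5a, change *study device* to *study procedure*.
3. In the rule for Table 14.3.5.1a, change *study device* to *study device or procedure*.
4. In SAP 10.1.4, say whether by-group serious-event tables will be produced. If they are, apply the corrected rules.

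The cost is SAP wording and the matching table specifications. No new data and no design change are needed. The edits should be made before the by-group outputs are produced, so that the split is fixed in advance.

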10.1.2. Handling of Missing or Partial Adverse Event Dates

Handling of Missing AE Start-dates (missing AE stop-dates are not filled)

Rules for assuming a full date for AEs with incomplete or missing start-dates are addressed below. In the unusual case that the month portion of an AE start-date is missing but the day portion is not missing, the day portion of the AE will be assumed to be missing. Likewise in the case where the year portion of an AE start-date is missing but the month and/or day portion is not missing, the month and/or day portion of the AE will be assumed to be missing. All missing portion(s) of the AE start-dates will be handled using the same rules.

- In the event that the day portion (and only the day portion) of the AE onset date is missing:
 - If the AE started in the same month and year as the study procedure, the AE onset date will be assumed to be the date of the study procedure (*i.e.*, Study Day 1);
 - Otherwise, the AE onset date will be assumed to be the 15th day of the given month and year, *e.g.*, XX-DEC-2005 → 15-DEC-2005 where XX represents an unknown value.
- In the event that the day and month portion (and only the day and month portion) of the AE onset date are missing:
 - If the AE started in the same year as the study procedure, the AE onset date will be assumed the study procedure (*i.e.*, Study Day 1);
 - Otherwise, the AE onset date will be treated as June 15th of the given year, *e.g.*, XX-XXX-2005 → 15-JUN-2005.

- In the event that the day, month, and year portion of the AE onset date are missing, the start-date of the AE will be assumed to be the study procedure (*i.e.*, Study Day 1).

Special Cases on Missing AE Start-dates

- If the assumed AE onset date using the above rules for handling of missing AE dates
 - is earlier than the screening date, the assumed AE onset date will be reset and assumed to be the screening date.
 - is later than the reported AE stop-date, the assumed AE onset date will be reset and assumed to be the AE stop-date.
 - is later than the database lock date and AE stop-date missing, the AE will be assumed to be a follow-up AE and not treatment-emergent.

Several Examples of Handling Missing AE Start-dates

Assume that the study procedure for a patient is 04-FEB-2005 and the Screening Date is 18-JUL-2004

- Example: The day portion (and only the day portion) of the AE onset date is missing:
 - If the AE onset date is XX-DEC-2004 then the assumed AE onset date is 15-DEC-2004.
 - If the AE onset date is XX-FEB-2005 then the assumed AE onset date is 04-FEB-2005, as the AE started in the same month and year as the study procedure.
- Example: The day and month portion (and only the day and month portion) of the AE onset date are missing
 - If the AE onset date is XX-XXX-2004:
 - then the assumed AE onset date is 15-JUN-2004 using the rules;
 - but this is a special case since the assumed date 15-JUN-2004 is before the patient's screening date 18-JUL-2004. Therefore, the assumed AE onset date will be reset and assumed to be 18-JUL-2004.
 - If the AE onset date is XX-XXX-2005 then the assumed AE onset date is 04-FEB-2005, as the AE started in the same year as the study procedure.
- Example: The day, month, and year portion of the AE onset date are missing (*i.e.*, if the AE onset date is XX-XXX-XXXX), then the assumed AE onset date is 04-FEB-2005).

